#### *9.2.2. Primary Endpoint*

The primary endpoint in this study will be the change from baseline in 24-hour cough frequency (geometric mean) after 14 weeks of intervention over placebo (day 98, visit 8) adjusted for baseline cough frequency (day 13, visit 2). The primary efficacy endpoint will be analysed using a generalised estimating equation modelling (GEE) analysis including the baseline cough frequency as a co-variate. Both FAS and PPS populations will be analysed.

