### **C. Objective Cough Monitoring:**

Participants will be asked to wear an ambulatory cough monitor (VitaloJAK™, Vitalograph, UK) for 24 hours, 3 times during the study: Visits 2, 5 and 8. This involves attaching an air microphone to the lapel of the clothing and a chest sensor on the sternum. The VitaloJAK cough recorder is worn around the waist of the subject. Subjects will wear the cough monitor for a continuous 24 hours and return the following day for the procedures for the next visit. Subjects will be informed not to have a shower during this period to prevent the air microphone and chest sensor being damaged by water.

The VitaloJAK cough monitor is a non-invasive, battery operated, and custom-built validated recording device and microphone intended to acquire, record and store ambulatory cough sounds from participants for 24 hours. Briefly, this consists of a digital data logger recording sounds at a sample rate of 8 kHz, with 16-bit resolution and in Waveform Audio File format, which is a commonly used uncompressed sound file format. Recordings will be transferred to a personal computer; silences and background noise will be removed by using validated, custom-written software, and cough sounds will be counted by using an audio editing package. The number of coughs will be expressed as coughs per hour and added up to give a cough count for a 24-hour period, awake cough frequency, and night-time cough frequency.

The cough monitor is an audio recording device and will record all sound including conversations. The cough monitor microphones capture speech in the local vicinity in addition to cough sounds. Therefore, it is possible that despite processing of the cough recording by customised software, some of the participant’s conversations are also

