### **5.13. Blinding and Randomization**

Subjects will be assigned to one of the two possible treatment arms generated by a computer-generated randomisation schedule prepared by McMaster University, with a ratio of 1:1, mepolizumab or placebo. As there is a known imbalance in the prevalence and cough rates, the study will include sex as a randomisation factor. This will mitigate the possibility of the intervention being confounded by sex differences in the 2 arms of the study. Blinded study drug supplies will be provided in sequentially numbered identical syringes in accordance with the randomisation schedule and dispensed by a pharmacist who shall not be delegated any other role in the study. Subjects, investigators, research staff (with the exception of the pharmacist) and the sponsor will be masked to the treatment sequence assignment. A sealed code-break envelope for each subject containing details of the treatment allocated will be kept in a locked safe at the study site.

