### **5.14. Premature Withdrawal/Discontinuation Criteria**

During the process of informed consent, participants will be informed that they may withdraw from the study at any time voluntarily without giving any reason and without their medical care or legal rights being affected. If a participant decides to withdraw from the study early, the data collected will be retained with their permission. If the participant declines to give permission for the data collected to be retained, it will be destroyed.

It is also possible that patients may develop an upper respiratory tract infection and as a result the subjects will be withdrawn. If this occurs, then the participant will be offered a re-screen after 4 weeks from the end of symptoms.

The study may be terminated if there is a determination of futility.

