### 9. Statistical Plan

#### 9.1. Sample Size Estimation

It is assumed that 60 subjects will be screened to randomize 30 subjects, and 15 will be randomized to complete each treatment arm in 1:1 ratio. This is a proof-of-concept study investigating the effectiveness of mepolizumab on objective cough rates in patients with

eosinophilic asthma or NAEB. As such, no formal power calculation can be currently performed. The sample size is therefore based on previous similar pilot studies using cough monitoring as an endpoint (36, 37).

With 15 patients per arm, this study will have 80% power with an alpha of 5% to detect an estimated 20% greater reduction in 24hr cough frequency compared with the placebo arm, assuming a log standard deviation of 0.60. A clinically relevant reduction in cough frequency of 20% was established following a recent phase 3 studies of gefapixant in refractory chronic cough which showed a 20% reduction over placebo as significant (38). The data from this study will be used to estimate the sample size required for any future multi-centre studies.

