## 9.2. Statistical Analysis

### 9.2.1. General Considerations, Assumptions, and Definitions

This study will generate data of demographics, LCQ scores, modified Borg scores for sensations and cough, methacholine (PC20), blood eosinophils, sputum eosinophil, total and activated mature eosinophils in sputum and blood. These continuous variables will be presented and analysed as either mean (S.D), median (IQR) or geometric mean (geometric S.D). It is generally assumed that cough frequency data will not be normally distributed, and hence cough frequency data will be log transformed and shown as geometric mean (geometric S.D). Statistical significance will be set at  $p<0.05$ .

For the purposes of analysis, the populations for analyses will be defined as:

1. Full analysis set (FAS): consists of all subjects randomized to a treatment arm, who received at least one dose of investigational product irrespective of their protocol adherence and performed at least one period of 24-hr cough monitoring before and one after treatment.
2. Per Protocol Set (PPS): consists of all patients in who did not have any major protocol deviations, and provided cough frequency recording at baseline, 4 weeks and 8 weeks after treatment.

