#### *9.2.3. Secondary Endpoint*

Comparison of cough frequency, LCQ, mBorg, sputum and blood eosinophilia, will be performed using the same statistical approach as for the primary outcome including data after week 8 and week 14 of intervention. The proportion of subjects with a reduction in cough frequency more than 30% in the mepolizumab and placebo groups will be analysed using a chi-squared test.

The effect of intervention on changes in inflammatory cells in blood and sputum and methacholine PC20 will be compared to baseline measurements in the mepolizumab/placebo group. This will be analysed using either an independent t-test or Mann-Whitney test depending on the normality of data.

Changes in objective cough frequency will be correlated with changes in serum and sputum eosinophilia and all subjective patient reported outcomes.

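### The primary GEE in about 30 participants has no stated variance estimator, reference distribution or small-sample correction, and leaves out sex, the randomisation factor

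*Combined protocol and SAP*

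**What the plan says.** - Section 9.2.2 sets the endpoint as the change in 24-hour cough frequency at week 14. On the model it says: "The primary efficacy endpoint will be analysed using a generalised estimating equation modelling (GEE) analysis including the baseline cough frequency as a co-variate". Both the FAS and the PPS are analysed.
- Section 9.2.1 adds log transformation of cough frequency and a threshold: "Statistical significance will be set at" p<0.05.
- Section 5.13 says: "As there is a known imbalance in the prevalence and cough rates, the study will include sex as a randomisation factor". Sex is not named in 9.2.2 or 9.2.3.
- Section 5.11 C schedules cough recordings "3 times during the study: Visits 2, 5 and 8", that is, at baseline, week 8 and week 14. To be in the FAS (9.2.1), a treated participant must have "performed at least one period of 24-hr cough monitoring before and one after treatment".
- Section 5.14 foresees that participants may develop "an upper respiratory tract infection and as a result the subjects will be withdrawn".
- Section 9.2.3 applies to cough frequency, LCQ, mBorg and eosinophilia the "same statistical approach as for the primary outcome including data after week 8 and week 14 of intervention".
- Sections 9.1 to 9.4 do not mention a variance estimator, reference distribution, working correlation or small-sample correction.

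**The concern.** A GEE is normally reported with a sandwich variance and a z statistic, both of which rely on a large number of independent participants. Thirty is not large: the uncorrected sandwich underestimates the variance, and z ignores that the variance was estimated. An analyst who follows 9.2.2 literally can therefore obtain a test that does not hold the declared 5%. Section 9.4 requires an amendment for deviations from the plan, but a choice the plan leaves open is not a deviation, so it could be made after unblinding.

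Two related gaps sit beside this:

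- **Sex.** It is used to balance the arms but not in the model. This is a question of precision, not of inflated error.
- **Week 8.** Section 9.2.2 does not say whether the week-8 recording enters the primary model. A participant withdrawn after week 8 is in the FAS without a week-14 value, and section 9.3 gives no method for that.

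At stake are the error rate of the primary test, the honesty of its interval, and the same properties for the secondary outcomes that reuse the approach.

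**Working it through.** **Inputs from the plan.** 15 per arm, 1:1; nominal 5%, taken as two-sided; log-scale outcome; log SD 0.60 (9.1: "assuming a log standard deviation of 0.60"). Section 9.1 does not say whether 0.60 is a between-subject or a residual SD, so both were tried. The 80% power stated there does not reproduce: |ln 0.8| = 0.223, SE = 0.60 × √(2/15) = 0.219, ratio 1.02, power about 17%. That is a separate matter and nothing below relies on it.

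**Assumed, because the plan gives no figures.** Baseline to follow-up correlation r of 0.5 to 0.8; week 8 to week 14 correlation 0.8 to 0.85; two-thirds female (section 1.2 says chronic cough is twice as common in females); residual sex effect 0 to 0.4 log units.

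**Step 1: exact results for a model-based SE with z.** With intercept, treatment and baseline, n = 30 leaves 27 df.

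- Divisor n−p: P(|t₂₇| > 1.96) = 6.04%.
- Divisor n: P(|t₂₇| > 1.96 × √(27/30)) = 7.39%.
- With sex added (26 df): 6.08% and 7.96%.

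**Step 2: simulated type I error.** Null trials, 15 per arm, no residual sex effect; ranges cover two independent sets of simulations, week 14 alone and weeks 8 and 14 together.

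| Inference | Sex omitted |
|---|---|
| Uncorrected sandwich, z | 7.0–8.0% (about 7.5%) |
| Uncorrected sandwich, t | 5.9–6.7% |
| Model-based or ANCOVA, t | 4.6–5.5% |
| Kauermann-Carroll, t | 4.7–5.4% |
| Mancl-DeRouen, z | 4.5–5.0% |
| Mancl-DeRouen, t | 3.6–4.1% (conservative) |

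With sex added, the uncorrected sandwich with z gives 7.4–8.6%. At 12 per arm it gives 8.2–8.4% without sex and 8.9–9.4% with sex. A standard package's default GEE (robust SE, z) gave 7.1% in 6,000 null trials at r = 0.7, against 4.7% for ANCOVA with t on the same data.

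**Step 3: interval width.** The expected ratio of sandwich-z to t half-widths is close to (1.96/2.052) × √(27/30) = 0.906. Simulated half-widths in log units were:

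- r = 0.5: 0.355 against 0.393
- r = 0.7: 0.293 against 0.324
- r = 0.8: 0.246 against 0.272
- 0.60 as residual SD: 0.410 against 0.453

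The ratio is about 0.904 each time, so the interval is 9.6% too narrow.

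**Step 4: sex.** A residual sex effect g with two-thirds female adds g² × 2/9 to the residual variance when sex is left out. At r = 0.7 the residual SD is 0.60 × √(1 − 0.49) = 0.428. For g = 0.3 the widening is √(1 + 0.09 × (2/9)/0.428²) = 1.053.

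| Residual sex effect | Widening of t interval, r 0.7 (r 0.5–0.8) | Widening if 0.60 is residual SD | Sandwich-z error, sex omitted, r 0.7 |
|---|---|---|---|
| 0.2 | 2% (2–4%) | 1% | 6.9% |
| 0.3 | 5% (4–8%) | 3% | 6.1% |
| 0.4 | 10% (7–14%) | 5% | 5.3% |

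The error falls because the arms are balanced on sex while the model treats sex variation as noise. If baseline cough carries the whole difference (0.5 log units tried), adding sex gains nothing: 0.323 without it, 0.325 with it.

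**Step 5: week 8.** With complete data, a two-visit mixed model (unstructured covariance, Kenward-Roger) gives the same week-14 result as ANCOVA. With week 14 missing at random in 1, 2 or 3 per arm at r = 0.7, its half-widths are 0.333, 0.343 and 0.355, against 0.338, 0.353 and 0.372 for ANCOVA, which is therefore about 1.5%, 3% and 5% wider. The mixed model's type I error was 5.2–5.4%.

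**The case against.** The strongest reply is that 7.5% belongs to an analysis the plan does not prescribe. Nothing requires an uncorrected sandwich with z, and a model-based SE with t, or a Mancl-DeRouen variance with z, would hold about 5%. The two main points also offset each other: a residual sex effect large enough to cost precision brings the sandwich-z error back towards 5% (and below it for still larger effects), and with no such effect the omission of sex costs nothing. The residual sex effects are assumed, and baseline cough may absorb any sex difference. The trial is a proof of concept, and sizing later studies depends on the SD and effect estimate, which z or t does not change. Section 9.2.2 names week 14 only, which can be read as excluding week 8 from the primary model.

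Much of this stands as limits on size. The error rate is conditional, the two points are never both at full size, and the week-8 gain is small. It is also true that 9.2.3 goes on to assign inflammatory cells to a t-test or Mann-Whitney test, so the method for eosinophils is itself unclear.

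It does not remove the gap. The plan declares significance at p<0.05 without fixing a procedure that delivers it, and a common software default does not. The effect estimate carried into later planning needs an interval with its stated coverage.

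**Conclusion.** The concern holds. The primary model is under-specified for a trial of this size. If it is run as an uncorrected sandwich GEE with z, and sex has little residual effect, the type I error is about 7.5% and the 95% interval covers about 92.5%. Across the unstated choices the error runs from about 4% (Mancl-DeRouen with t) to about 7.5%, or about 8% if sex is added without a correction.

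Omitting sex is a separate loss of precision, 2 to 10% in interval width at r = 0.7 for assumed residual effects of 0.2 to 0.4 log units, and none if baseline carries the difference. These figures rest on the assumed correlations, sex share and sex effects listed above. The omissions themselves are plain from the text. This should be corrected, but the excess error is modest and conditional.

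**What to change.** State in section 9.2.2 that the log 24-hour cough rate is modelled on treatment, log baseline and sex with small-sample inference, and choose one of these before unblinding:

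1. **Preferred.** A mixed model for weeks 8 and 14 together, with unstructured covariance, covariate effects by visit and Kenward-Roger degrees of freedom. The week-14 contrast is primary. FAS participants with only a week-8 recording stay in.
2. **Week-14 ANCOVA with t.** 30 − 4 = 26 residual df. State that it drops participants without a week-14 recording.
3. **GEE.** Name the working correlation and the visits, and use a Kauermann-Carroll variance with a t reference.

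Add sex and the correction together, because sex with an uncorrected sandwich and z makes the error worse. Carry the same choice into section 9.2.3, and say there which method applies to eosinophils.

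The cost is SAP wording and standard software, with no new data. Sex uses one degree of freedom (interval about 0.2–0.3% wider if it has no residual effect). The reported interval will be about 10% wider than the uncorrected sandwich GEE would show. Option 1 needs a covariance model for two visits.

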#### *9.2.3. Secondary Endpoint*

Comparison of cough frequency, LCQ, mBorg, sputum and blood eosinophilia, will be performed using the same statistical approach as for the primary outcome including data after week 8 and week 14 of intervention. The proportion of subjects with a reduction in cough frequency more than 30% in the mepolizumab and placebo groups will be analysed using a chi-squared test.

The effect of intervention on changes in inflammatory cells in blood and sputum and methacholine PC20 will be compared to baseline measurements in the mepolizumab/placebo group. This will be analysed using either an independent t-test or Mann-Whitney test depending on the normality of data.

Changes in objective cough frequency will be correlated with changes in serum and sputum eosinophilia and all subjective patient reported outcomes.

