### **7.2. Secondary Outcomes**

In patients with refractory chronic cough with airway eosinophilia to measure changes from baseline after 8 and 14 weeks of treatment with mepolizumab compared with placebo of:

1. Awake cough frequency (coughs/hr)
2. Night-time cough frequency (coughs/hr)
3. Percentage of participants with a reduction in 24-hour cough frequency of  $\geq 30\%$

4. All cough outcomes by disease group (asthma and NAEB)
5. Cough severity and intensity of sensations (itch, tickle, irritation, urge to cough on a modified Borg Scale)
6. Quality of life measured using the Leicester Cough Questionnaire (LCQ)
7. Blood eosinophils
8. Sputum Eosinophilia (% cell count)

To determine changes from baseline after 14 weeks of treatment with mepolizumab compared with placebo of:

1. Methacholine PC20
2. Total, activated mature eosinophils, eosinophil progenitors in blood and sputum (Flow cytometry) and related transcriptomics.

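### Changes in inflammatory cells and PC20 are tested without baseline adjustment, by a test picked on an unspecified normality check, and *inflammatory cells* is undefined, so its boundary with the GEE outcomes is unclear

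*Combined protocol and SAP*

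**What the plan says.** Section 9.2.3 has two relevant paragraphs.

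- **First paragraph.** "Comparison of cough frequency, LCQ, mBorg, sputum and blood eosinophilia, will be performed using the same statistical approach as for the primary outcome", with data from weeks 8 and 14. Section 9.2.2 defines that approach as a "generalised estimating equation modelling (GEE) analysis including the baseline cough frequency as a co-variate".
- **Second paragraph.** "The effect of intervention on changes in inflammatory cells in blood and sputum and methacholine PC20 will be compared to baseline measurements". The method follows: "This will be analysed using either an independent t-test or Mann-Whitney test depending on the normality of data". No covariate, normality test, threshold, scale or time point is given. The first sentence could suggest a within-arm comparison with baseline. Both named tests compare independent groups, however, so the workable reading is a between-arm comparison of changes.

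Section 7.2 has two lists of secondary outcomes. The list for weeks 8 and 14 includes blood eosinophils and "Sputum Eosinophilia (% cell count"). The list for week 14 only holds methacholine PC20 and "Total, activated mature eosinophils, eosinophil progenitors in blood and sputum (Flow cytometry) and related transcriptomics".

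Baselines exist for the second list. Flow cytometry is done at Visits 3 and 9 (Sections 5.11.B and 5.11.E) and PC20 at Visits 1 and 9 (Section 5.11.D). Section 4 lists inflammatory cells as a single secondary objective and has no separate objective for the effect of treatment on eosinophil counts.

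**The concern.** Two things are left open.

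First, the second paragraph uses a less precise method than the first for outcomes that also have a baseline. It also lets the observed data choose the test, under a rule that two analysts could apply differently.

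Second, the boundary between the paragraphs is not drawn. If *inflammatory cells* includes eosinophil counts, as Section 4 suggests, those counts fall under both methods and nothing says which one governs.

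The hypothesis in Section 2 is that mepolizumab lowers airway eosinophilia and thereby cough. With 15 per arm, a null cough result will be hard to interpret unless the cellular effect is estimated by one efficient method fixed in advance.

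**Working it through.** The documents give no SD, effect size or baseline correlation for cells or PC20, so there is no plan figure to reproduce. The power statement in Section 9.1 concerns cough frequency and does not bear on this point. Only n = 15 per arm (Section 9.1) comes from the documents; every r, SD and effect below is assumed.

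**1. Is there an overlap?**

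| Outcome | Section 7.2 timing | 9.2.3 first paragraph | 9.2.3 second paragraph |
|---|---|---|---|
| Blood eosinophils | weeks 8 and 14 | named | only if the term is an umbrella |
| Sputum eosinophil % | weeks 8 and 14 | named | only if the term is an umbrella |
| Flow-cytometry cells | week 14 | not named | fits |
| PC20 | week 14 | not named | named |

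The text allows both readings. The lower two rows have no baseline covariate under either.

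**2. Precision lost.** Let σ² be the common variance at baseline and follow-up, r their correlation and n the number per arm.

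- Change score: Var = (2/n) · 2σ²(1 − r)
- Baseline-adjusted: Var ≈ (2/n) · σ²(1 − r²)
- Ratio: (1 − r²) / [2(1 − r)] = (1 + r)/2

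| Assumed r | Ratio | Reduction | Change-score n matching 15 adjusted |
|---|---|---|---|
| 0.3 | 0.65 | 35% | 15/0.65 = 23.1 |
| 0.5 | 0.75 | 25% | 15/0.75 = 20.0 |
| 0.7 | 0.85 | 15% | 15/0.85 = 17.6 |

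Error degrees of freedom fall from 30 − 2 = 28 to 27 with baseline, and to 26 with sex as well.

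**3. Power.** A simulation (15 per arm, 6,000 runs per setting, normal data, assumed effect 0.8 SD) compared ANCOVA at one time point with a t-test or Mann-Whitney test on changes, selected by Shapiro-Wilk. For r = 0.3, 0.5 and 0.7, power was 59%, 66% and 84% adjusted, against 44%, 56% and 78% selected.

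**4. How far chance picks the test.** What is checked for normality is the change. Samples of 15 were simulated 4,000 times per setting from lognormal values with r = 0.5 and 0.7 and no treatment effect. Shapiro-Wilk at 5% rejected raw changes as follows:

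| Log SD | Rejected, one arm of 15 |
|---|---|
| 0.5 | 19–20% |
| 0.8 | 40–41% |
| 1.0 | 54–56% |

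Log-scale changes, which are exactly normal here, were rejected about 5% of the time. The choice of test therefore depends on a scale that the plan does not state and, on the raw scale, largely on the sample drawn.

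**5. Only if the paragraphs overlap.** With both analyses run on one endpoint and no true effect, at least one p < 0.05 arose in 7.2–7.8% of simulated trials (r = 0.3 to 0.7, normal or lognormal data). Two independent tests would give 1 − 0.95² = 9.75%. With the 0.8 SD effect and normal data, the two p-values fell on opposite sides of 0.05 in 10–25% of trials.

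**The case against.** The best defence is that Section 9.2.3 mirrors Section 7.2. The first paragraph speaks of eosinophilia at weeks 8 and 14. The second uses a different term and pairs it with PC20, as the week-14 list does. On that reading each outcome has one analysis. A reader might infer that blood and sputum eosinophils are certain to have two methods and two p-values; the documents do not establish that. What stands against the defence is that the second paragraph mentions neither flow cytometry nor a time point, and that Section 4 uses the same term as an umbrella.

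A reader might also infer that baseline is thrown away. It is not: the tests are on changes, so baseline enters by subtraction and only the covariate adjustment is lost. Both approaches are valid under randomisation, so this is a gain in efficiency and clarity and not the removal of a bias.

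The variance formula has limits, and these stand. It assumes equal variance at both times, which is doubtful on the raw scale for a drug expected to lower eosinophils. It ignores the degree of freedom spent, and it does not describe the Mann-Whitney test.

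For PC20 a rank method has real merit. The test stops at a top concentration, and Section 1.2 says that NAEB patients lack airway hyper-reactivity, so many values will be censored. That argues for choosing such a method in advance, not for choosing it after a normality check.

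**Conclusion.** The point holds as a near-free improvement to secondary analyses; the primary endpoint is untouched. The lack of baseline adjustment and the unspecified normality rule are in the text under either reading of *inflammatory cells*. The overlap with the GEE outcomes is possible but not certain, so the error rates in step 5 are conditional.

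The expected gain is a variance 25% lower at r = 0.5 or 15% lower at r = 0.7, assuming equal variances on the analysis scale. It shrinks as r approaches 1.

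**What to change.** 1. State that blood eosinophil counts and sputum eosinophil percentage are analysed only by the GEE of the first paragraph, at weeks 8 and 14. Use the log scale, with a small fixed offset for zeros and each outcome's own baseline as covariate.
2. Limit the second paragraph to flow-cytometry cells and PC20, and delete the normality-dependent choice. For the cells, regress the log post-treatment value on arm, log baseline (Visit 3) and sex, which is the randomisation factor in Section 5.13. Report a ratio of geometric means.
3. For PC20, use the Visit 1 baseline and pre-specify how values above the top concentration are handled, for example by a baseline-adjusted censored or rank-based analysis. Section 5.11.D gives both 16 and 32 mg/mL as the upper limit. The two statements must be reconciled, because they set the censoring point.
4. Define *inflammatory cells*, or replace the term with the names of the outcomes.

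The cost is a change of wording, made as a protocol amendment (Section 9.4) before unblinding, and one or two degrees of freedom. All the values are already collected.

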### *Treatments for cough in asthma and non-asthmatic eosinophilic bronchitis*

Both asthma and NAEB are associated with airway eosinophilia, but in the latter, there is no evidence of increased airway hyper-reactivity or variable airflow limitation, and cough is the predominant symptom. This has led to guidelines recommending a trial of treatment with ICS. However, the strength of the recommendation is weak due to a lack of evidence showing reduction in objective coughs rates in placebo-controlled studies (23). The use of ICS is well established in asthma from the large phase 3 randomized controlled trials (RCT), however, cough is not independently assessed in most studies, and current asthma questionnaires such as the asthma control questionnaire (ACQ) do not capture cough as a symptom. In patients with asthma or NAEB, use of inhaled corticosteroids can also make coughing worse, occasionally leading to use of low-dose oral corticosteroids. This can result in long term side effects which are intolerable to patients.

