#### **Secondary Objectives:**

1. To determine the effects of mepolizumab on:

- i. Awake /Night-time cough frequency
- ii. Intensity of irritant sensations
- iii. Quality of life
- iv. Airway hyper-responsiveness
- v. Inflammatory cells

All the above secondary objectives will also be analysed based on disease group, i.e., asthma and NAEB.

[figure not shown]
2. The relationship between change in cough frequency and change in eosinophils

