#### **D. Methacholine Challenge Test**

Methacholine is a synthetic form of acetylcholine and therefore causes smooth muscle contraction. It is commonly used in clinical practice to exclude asthma, but also as a measure of airway hyper-responsiveness. It involves giving nebulised methacholine in doubling concentrations from 0.0625 mg/mL up to 16 mg/ml via the 2-minute tidal breathing method. At each concentration, FEV1 is measured 30s and 90s after the end of each inhalation. The % fall in FEV1 from baseline is calculated after each dose using the best FEV1 and the test is terminated once a 20% fall in FEV1 (PC20) is documented or the maximum concentration of 32 mg/mL is reached. Patients with a methacholine PC20<16mg/ml will be considered to have asthma. The methacholine PC20 will be assessed at Visit 1 and Visit 9. Information about which medication to stop prior to the test will be given to the patient.

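### The PC20 comparison in section 9.2.3 pools NAEB with asthma and has no rule for tests that reach the top concentration, so its estimate is pulled toward zero

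*Combined protocol and SAP*

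**What the plan says.** Section 4 lists airway hyper-responsiveness among the secondary objectives and adds: "All the above secondary objectives will also be analysed based on disease group, i.e., asthma and NAEB". Section 7.2 makes PC20 a week-14 outcome, introduced by "To determine changes from baseline after 14 weeks of treatment with mepolizumab compared with placebo of". The only disease-group item in that section concerns the cough outcomes.

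Section 9.2.3 says that "methacholine PC20 will be compared to baseline measurements in the mepolizumab/placebo group", and then: "This will be analysed using either an independent t-test or Mann-Whitney test depending on the normality of data". Since the test is for independent groups, I read this as a between-arm comparison of change. No subset, baseline term or censoring rule is given. The baseline-adjusted approach of the primary analysis is extended in the same section to cough frequency, LCQ, mBorg and eosinophils, but PC20 is not in that list.

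Section 5.11 D defines the disease groups: "Patients with a methacholine PC20<16mg/ml will be considered to have asthma". Section 1.2 says of NAEB that "there is no evidence of increased airway hyper-reactivity or variable airflow limitation". On the test itself, section 5.11 D describes "doubling concentrations from 0.0625 mg/mL up to 16 mg/ml via the 2-minute tidal breathing method" but ends the test at a 20% fall or when "the maximum concentration of 32 mg/mL is reached".

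**The concern.** A participant in whom the top concentration does not produce a 20% fall has no measured PC20, only a lower bound. NAEB participants are the ones most likely to be in that position at baseline, because anyone below 16 mg/mL is classed as asthma. If such a participant improves further, the recorded change is zero. Entered into a two-group test, these zeros shrink the mean difference in proportion to the NAEB share. The reported effect on hyper-responsiveness would then depend on the recruitment mix as well as on the drug.

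Asthma participants who improve past the ceiling by Visit 9 are cut off too, so the problem is not confined to NAEB. Disease group is also not a randomisation factor (section 5.13 names sex only), so NAEB counts can differ between arms and add noise to the pooled comparison. Section 9.1 intends the data to inform later studies, and for that purpose the size of an estimate matters.

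**Working it through.** The documents give no power, SD or expected effect for PC20, so there is no stated figure to reproduce. They also do not give the NAEB share. The effect, SD, shares and baseline distributions below are assumptions; 15 per arm is from section 9.1 and the two ceilings are from section 5.11 D.

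**Step 1, where NAEB participants start.** PC20 below 16 mg/mL means asthma, so a non-asthmatic participant has PC20 of at least 16 mg/mL at Visit 1. On the log2 scale that is 4 or more. The ceiling C is log2 16 = 4 or log2 32 = 5, depending on which statement governs. The recorded value is min(true log2 PC20, C).

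**Step 2, simple mixture.** Suppose every NAEB value is at the ceiling at both visits. With NAEB share q and a true asthma effect d, the pooled difference is (1 − q) × d. For d = 1 doubling and 15 per arm:

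- 3 NAEB per arm: 12/15 = 0.80
- 5: 10/15 = 0.67
- 7: 8/15 = 0.53
- 9: 6/15 = 0.40

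**Step 3, simulation with both ceilings.** Asthma baselines are uniform on log2 from 0.5 to 16 mg/mL and NAEB true baselines from 16 to 64 mg/mL. SD of change is 1.0 doubling and the true gain is 1.0 in all treated participants, with 2,500 replicates. Power is for the two-sided 5% t-test.

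| Ceiling (mg/mL) | NAEB per arm | Pooled difference | Asthma-only difference | Changes exactly zero | Power, pooled / asthma only |
|---|---|---|---|---|---|
| 16 | 3 | 0.72 | 0.88 | 18% | 60% / 60% |
| 16 | 5 | 0.61 | 0.87 | 29% | 53% / 52% |
| 16 | 7 | 0.50 | 0.84 | 41% | 41% / 39% |
| 16 | 9 | 0.40 | 0.84 | 53% | 32% / 29% |
| 32 | 3 | 0.85 | 0.97 | 8% | 70% / 66% |
| 32 | 5 | 0.75 | 0.95 | 13% | 61% / 55% |
| 32 | 7 | 0.66 | 0.94 | 19% | 56% / 45% |
| 32 | 9 | 0.59 | 0.96 | 24% | 52% / 35% |

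The asthma-only difference falls short of 1.00 because some asthma participants pass the ceiling at Visit 9. Restriction without a censoring rule is therefore not enough. The rank test does not help: with 5 NAEB per arm and a 16 mg/mL ceiling, pooled Mann-Whitney power is 47% against 53% for the t-test.

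**Step 4, smaller SD.** With SD of change 0.75 and one third to two thirds NAEB, the pooled estimate is 0.59 to 0.34 doublings at a 16 mg/mL ceiling and 0.75 to 0.52 at 32. Baseline-adjusted censored regression in participants with baseline PC20 below 16 mg/mL gives about 0.94 to 1.03.

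**Step 5, does restriction buy power?** Take the mixture of Step 2 with q = 1/3 and SD 1.0.

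- Variance of change is (1 − q) × 1² = 0.667 on placebo and 0.667 + q(1 − q) × 1² = 0.889 on treatment. The average is 0.778, so SD is 0.882.
- Pooled: 0.667 / (0.882 × √(2/15)) = 2.07, power Φ(2.07 − 1.96) = 54%.
- Asthma only, 10 per arm: 1 / √(2/10) = 2.24, power Φ(2.24 − 1.96) = 61%.

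At SD 1.5 the same comparison is 30% against 32%. The largest gain over the shares in Step 2 is about 8 points (33% against 41% with 9 NAEB per arm). In Step 3, where NAEB values are not all fixed at the ceiling, restriction gives equal or lower power.

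**The case against.** The strongest reply is that an asthma-specific look at PC20 is already planned. Section 4 covers airway hyper-responsiveness and promises analysis by disease group. That stands, and a reader who infers that the plan has no such analysis would be wrong. But it is an addition to the pooled test. Section 9.2.3 does not specify it, section 7.2 confines disease-group analysis to cough, and it would still lack a censoring rule.

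Three other stronger readings are not supported:

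- *Every NAEB participant is censored at baseline and cannot improve.* This follows only if the test stops at 16 mg/mL. At 32 mg/mL, values between 16 and 32 are measurable and the dilution is smaller, though still present.
- *PC20 will be analysed on the raw scale.* Section 9.2.1 lists PC20 among variables that may be summarised and analysed by geometric mean. The plan allows a log scale but does not commit to it.
- *The pooled test costs power that restriction would restore.* Step 5 does not show this; fewer participants can mean less power.

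It is also fair to say that a censored-regression model in perhaps 5 to 10 participants per arm is demanding for one secondary outcome of a proof-of-concept study. A likelihood-ratio test from that model rejected a true null in 9 to 10% of simulated trials. This argues for a re-randomisation p-value and modest claims. It does not justify leaving the ceiling unaddressed.

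**Conclusion.** The concern holds as a bias in the estimate and a gap in specification. Followed as written, section 9.2.3 gives a PC20 difference shrunk toward zero by an amount that depends on the NAEB share and on an unsettled ceiling. For a true gain of one doubling, with one third to two thirds NAEB and SD 0.75, the pooled figure is about 0.6 to 0.3 doublings at 16 mg/mL and about 0.75 to 0.5 at 32.

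The direction follows from the protocol's own definitions. The size rests on assumed effect, SD, NAEB share and baseline distributions, none of which the documents give. A null or small pooled result could not be read as absence of effect in asthma. The primary cough endpoint is unaffected.

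**What to change.** 1. In section 5.11 D, reconcile the two statements of the top methacholine concentration, so that the censoring point is defined.
2. In section 9.2.3, analyse log2 PC20 at Visit 9 with arm and baseline log2 PC20 as terms. Treat values above the reconciled top concentration as right-censored.
3. Make participants with baseline PC20 below 16 mg/mL the main PC20 estimate. This carries out the disease-group intention of section 4 and uses the cut-off of section 5.11 D. If a Tobit model is used, take the p-value from a re-randomisation test.
4. Report the baseline-adjusted comparison in all participants as supportive and the NAEB group descriptively. Align section 7.2 with section 4 on which outcomes are analysed by disease group.

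The cost is a few lines of plan text and slightly more analysis work; no new data or visits are needed. Section 9.4 requires an amendment for a departure from the plan, so this is best settled before unblinding. The price in interpretation is that the main PC20 estimate applies to the asthma group only and rests on fewer participants, possibly with less power.
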